11.6.2.3 Maximum change from baseline

Maximum reduction from baseline in NPRS mean scores will be summarized. Number and percentage of subjects will be summarized for the week at which maximum reduction from baseline in NPRS mean scores was reached by treatment overall and within each study period. This will be repeated for Per Protocol and FAS populations.

In DDP: Table 14.2.4.1 to 14.2.4.2

11.6.2.3.1 *Mixed Effects Regression Model*

Mixed effects regression models will be used to compare the maximum reduction from baseline in NPRS mean scores. The model will have fixed effects for period and treatment. Baseline score within each period by treatment combination and time taken to reach maximum reduction will be included as covariates. A random effect for subject will be included to capture the repeated measures nature of the design. Least squares mean changes from baseline and corresponding 95% CI will be presented for LAT8881, Placebo and the difference between LAT8881 vs. placebo overall. The null hypothesis that the difference in least square mean changes from baseline between LAT8881 and placebo across study periods is 0 will be tested. Statistical significance will be declared if the p-value for the difference between treatments < 0.05. In DDP: Table 14.2.4.3, 14.2.4.4

```
proc mixed data=;  
  class <subject> <study period> <treatment>;  
  model <maximum reduction> = <baseline> <study period> <treatment> <time  
  to maximum reduction>;  
  random <subject> <subject>*<period>;  
  lsmeans <treatment>/ pdiff;  
run;
```

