13.5.1 NPRS

The primary efficacy endpoint is the absolute change from baseline mean NPRS score to the end of treatment NPRS score after LAT8881, compared with the change from baseline after placebo treatment.

Daily NPRS scores for all enrolled subjects will be listed only. Mean and standard deviation of scores during the baseline period and weeks 1, 2, 3 and 4, and the absolute and percentage change from baseline in each period, will be listed for each subject and summarised for LAT8881 and placebo treatments overall and within treatment sequence for all randomised subjects and for the PP population. The maximum change in mean NPRS from baseline to weeks 1, 2, 3 and 4, determined for each subject after LAT8881and placebo, will be listed and summarised.

Mixed effects regression models will be used to compare the absolute and percentage changes from baseline to the end of each treatment for the mean NPRS scores. The models will have fixed effects for period and treatment. Baseline mean pain score within each period by treatment combination will be included as a covariate. A random effect for subject will be included to capture the repeated measures nature of the design.

The models for the primary endpoint will be expanded to compare the absolute and percentage changes from baseline for the mean NPRS scores after 1, 2 and 3 weeks of dosing with IMP in each treatment period. The model will also include a fixed effect for week (1, 2, 3 and 4), the interaction between treatment and week to assess whether the change from baseline for each treatment is different.

The mean score at each visit, change from baseline, difference between treatments in the change from baseline and corresponding 95% confidence intervals will be presented. Comparisons will be declared statistically significant if p<0.05.

In PK subjects, NPRS scores at specified times up to 6 hours on Days 1, 28, 50 and 77 will be listed and summarised. Change from pre-dose values will also be listed and summarised. Changes over time will be analysed using the same modelling approach as for the primary endpoint.

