3.2 Secondary Objectives

1. *To investigate the effect of oral LAT8881 in NP compared with placebo at different timepoints (up to 6 hours) following a single dose and after 4 weeks treatment, as measured by the NPRS (PK subjects only)*
2. *To investigate the effect of oral LAT8881 on mean pain scores in NP compared with placebo after 1, 2 and 3 weeks of dosing, as measured by the NPRS*
3. *To determine the proportion of responders to oral LAT8881 in NP compared with placebo*
4. *To investigate the maximum effect of oral LAT8881 in NP compared with placebo, as determined by the maximum change from mean NPRS baseline after 1, 2, 3 or 4 weeks treatment*
5. *To evaluate the effect of oral LAT8881, compared with placebo, on functioning in subjects with NP when measured by the 7-item short form Brief Pain Inventory (BPI) Interference Scale*
6. *To evaluate the effect of oral LAT8881, compared with placebo, on pain symptoms in subjects with NP when measured by the short-form McGill Pain Questionnaire 2 (SF-MPQ-2)*
7. *To evaluate the effect of oral LAT8881, compared with placebo, on symptoms in subjects with NP, when measured by the Neuropathic Pain Symptom Inventory (NPSI)*
8. *To evaluate the effect of oral LAT8881, compared with placebo, on emotional functioning when measured by the Beck Depression Inventory-II (BDI-II)*

9. To evaluate the effect of oral LAT8881, compared with placebo, on overall health and quality of life in subjects with NP, when measured by the Patient Global Impression of Change (PGIC) scale
10. To determine the change from baseline in rescue medication use during oral LAT8881 administration, compared with placebo
11. To evaluate the safety and tolerability of oral LAT8881 in NP after a single dose and after four weeks treatment
12. To investigate the pharmacokinetics of twice daily oral LAT8881 in 15 subjects with NP after a single dose and after 4 weeks treatment with oral LAT8881

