10.16.2 Maximum Reduction

For NPRS scores, maximum reduction from baseline (that is, maximum negative change from baseline) for a subject within each study period will be flagged. Time to maximum change in days and week at which maximum reduction was attained will be included.

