11.6.2.4 Patient reported outcomes

Patient Reported outcomes: BPI, SF-MPQ-2, NPSI, BDI-II, PGIC will be considered for secondary efficacy analyses. All analyses will be repeated for Per-protocol and FAS populations.

11.6.2.4.1 *Descriptive Summaries*

Descriptive summaries of patient reported outcomes (BPI, SF-MPQ-2, NPSI, BDI-II) and absolute change from baseline results will be presented by treatment overall and within each study period. Visits to be included in this table are: Baseline, Week 4.

Descriptive summaries as well as number and percentage of subjects reporting each of the categories in PGIC scale (1 - Substantially worse, 2 - Moderately worse, 3 - Slightly worse, 4 - No change, 5 - Slightly improved, 6 - Moderately improved, 7 - Substantially improved) will be summarized by treatment overall and within each study treatment period.

The summaries will be repeated for Per-Protocol and FAS populations.

In DDP: Tables 14.2.5.1, 14.2.5.2, 14.2.6.1, 14.2.6.2, 14.2.7.1, 14.2.7.2, 14.2.8.1, 14.2.8.2, 14.2.9.1, 14.2.9.2

All patient reported outcomes will be listed.

In DDP: Listing 16.2.6.2 to 16.2.6.6

11.6.2.4.2 *Mixed Effects Regression Model*

Mixed effects regression models will be used to compare the absolute change from baseline to week 4 for the patient reported outcomes (BPI, SF-MPQ-2, NPSI, BDI-II, PGIC). The models will have fixed effects for period and treatment. Baseline score within each period by treatment combination will be included as a covariate for all endpoints except PGIC. A random effect for subject will be included to capture the repeated measures nature of the design. Least squares mean changes from baseline and corresponding 95% CI will be presented for LAT8881, Placebo and the difference between LAT8881 vs. placebo overall. The null hypothesis that the difference in least square mean changes from baseline between LAT8881 and placebo across study periods is 0 will be tested. Statistical significance will be declared if the p-value for the difference between treatments < 0.05.

In DDP: Tables 14.2.5.3, 14.2.5.4, 14.2.6.3, 14.2.6.4, 14.2.7.3, 14.2.7.4, 14.2.8.3, 14.2.8.4, 14.2.9.3, 14.2.9.4

```
proc mixed data=;  
  class <subject> <study period> <treatment>; model  
  <change> = <baseline> <study period> <treatment>;  
  random <subject> <subject>*<period>; lsmeans  
  <treatment>/ pdiff;  
run;  
Note that, PGIC will not have <baseline> in the model statement.
```

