11.7.3.4 Electrocardiogram Assessments

Number and percentage of subjects with overall findings (Normal, Abnormal Not CS and Abnormal CS) will be summarized by treatment overall and within each study period and visit. Percentages will be based on safety population.

In DDP: Table 14.3.6.1

ECG findings will be listed by treatment sequence, subject ID, treatment period and visit.

In DDP: Listing 16.2.9.3

12 Changes to Planned Analyses

- Mixed Effect Regression analyses for change from baseline in NPRS mean scores is combined for weeks 1-4 within the same model, instead of week 4 and weeks 1-3 separately as defined in study protocol.
- McNemar's test is included to compare proportion of subjects achieving $\geq 30\%$ and $\geq 50\%$ reduction in mean NPRS scores across study periods.
- Analysis of covariance is included to see the effect of treatment and placebo in maximum reduction from baseline adjusting for baseline NPRS mean scores and time taken to reach maximum reduction.
- Mixed Effect Regression analyses for change from baseline in NPRS mean scores including clinical diagnosis (PHN, DPN) and baseline [REDACTED] as additional covariates is

considered as secondary analyses instead of exploratory analyses since subgroups PHN and DPN were considered clinically relevant.

- PK Analyses is not included in this Statistical Analysis Plan, and will be done separately. PK Population is replaced with Per-Protocol population for subjects with NPRS assessments taken at timepoints in baseline and Week 4 visits.

13 Index of Tables, Listings and Graphs

Refer LAT-NP-001_Data Display Plan (Ver: 2.00) for the list of Tables, Listings and Graphs.

14 References

1. ICH. ICH Harmonized Tripartite Guideline: Statistical Principles for Clinical Trials E9. 1998.
2. ICH. ICH Harmonized Tripartite Guideline: Structure and Content of Clinical Study Reports E3. 1995.

15 Appendices

15.1 painDETECT questionnaire

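### The maximum-reduction model adjusts for time to maximum reduction, a consequence of treatment, so its treatment difference is not the randomised comparison and can be biased either way

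*SAP*

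**What the plan says.** SAP 3.2 sets the objective as the maximum effect of LAT8881 compared with placebo, "as determined by the maximum change from mean NPRS baseline after 1, 2, 3 or 4 weeks treatment". Any of the four weeks may supply the maximum.

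SAP 10.16.2 takes the largest negative change from baseline within each period as the outcome and adds: "Time to maximum change in days and week at which maximum reduction was attained will be included". Under SAP 10.15.1 the weekly scores behind both variables are means of on-treatment diary ratings.

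On the model, SAP 11.6.2.3.1 states: "The model will have fixed effects for period and treatment". It continues: "Baseline score within each period by treatment combination and time taken to reach maximum reduction will be included as covariates". The PROC MIXED code carries the same time term, and significance is declared on the treatment difference at p < 0.05.

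The protocol planned less. Under its Section 13.5.1 the maximum change, "determined for each subject after LAT8881and placebo, will be listed and summarised". SAP Section 12 discloses the added model as "adjusting for baseline NPRS mean scores and time taken to reach maximum reduction" and gives no reason for the time term. The unadjusted description is kept in SAP 11.6.2.3: "Maximum reduction from baseline in NPRS mean scores will be summarized".

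**The concern.** Baseline pain is fixed before dosing in each period, so adjusting for it keeps the randomised comparison and improves precision. Time to maximum reduction differs on both counts. It is observed after randomisation, and it is a by-product of the series that yields the outcome. If LAT8881 changes when the best week falls, conditioning on that week compares subject-periods that randomisation did not make comparable, and it removes or adds part of the effect.

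The adjusted difference is the only planned inferential result for this objective, so its p-value would be read as the answer to a question that the model does not ask.

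**Working it through.** **The plan's own figure.** Protocol 13.2 and the synopsis give SD 2, correlation 0.5, a 1-unit difference, two-sided 5%, 90% power and 20% dropout.
- SD of the within-subject difference = sqrt(2 × 2² × (1 − 0.5)) = 2.0.
- Normal approximation: n = ((1.960 + 1.282) × 2 / 1)² ≈ 42.0, so 43. Paired-t power at n = 44 is 0.900.
- 44 / (1 − 0.20) = 55.

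The stated 44 and 55 reproduce. The documents give no figure for the maximum-reduction model, so its behaviour was simulated on the same SD and correlation.

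**Simulation 1: change in the estimate when time is added.** Each trial had 44 subjects, two sequences and four weekly mean changes per period, with 1,000 trials per cell. Week 4 SD was 2 and between-period correlation 0.5.
- Assumed baseline: mean 6, SD 1.2, correlation 0.7, coefficient −0.3.
- Assumed placebo improvement: flat at 0.5, or building 0.3/0.5/0.65/0.75.
- Assumed variances: weekly residual 0.5 or 1.0 without individual slopes; residual 0.5 with slope variance 1.0 (1.0/4 = 25% of week 4 variance); residual 0.3 with slope variance 1.5 (1.5/4 = 37.5%).
- Model: baseline, period, treatment and random subject, by REML, with and without time. Time was linear because it is absent from the CLASS statement.

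| LAT8881 effect, weeks 1/2/3/4 | No slopes | Slopes 25% | Slopes 37.5% |
|---|---|---|---|
| Constant | 0% | 0% | 0% |
| Plateau 0.5/1/1/1 | 0-1% lower | 7% lower | 10-13% lower |
| Building 0.25/0.5/0.75/1 or 0/0.33/0.67/1 | 3-7% lower | 20-32% lower | 31-51% lower |
| Late 0/0/0.5/1 or 0/0/0/1 | 7-15% lower | 39-51% lower | 53-72% lower |
| Waning 1/0.75/0.5/0.25, 1/0.67/0.33/0 or 1/0.5/0/0 | −7% to +1% | 16-40% higher | 27-69% higher |

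Power for the 0.25/0.5/0.75/1 profile falls from 68-79% to 59-73% without slopes, and from 81-83% to 59-68% with 25% slopes. With no effect in any week, rejection is 4.4-6.2% with or without the covariate.

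**Simulation 2: why the sign changes.** This was set up separately, with subject variance 2, period and residual variances 0.5 each, and individual slope SD 0.25 per week. Limits come from 200,000 subjects.

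| Scenario (placebo flat unless stated) | True | Without time | With time | Coefficient of time | Difference in mean week of maximum |
|---|---|---|---|---|---|
| Constant +1 | 1.003 | 1.003 | 1.003 | 0.244 | 0.00 |
| Building to 1 | 0.688 | 0.688 | 0.545 | 0.288 | +0.50 |
| Waning 1 to 0 | 0.613 | 0.613 | 0.742 | 0.199 | −0.65 |
| Constant +1, placebo building to 1 | 0.318 | 0.318 | 0.464 | 0.293 | −0.50 |

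To rounding, adjusted = unadjusted − coefficient × difference in mean week:
- Building: 0.688 − 0.288 × 0.50 = 0.544.
- Waning: 0.613 + 0.199 × 0.65 = 0.742.
- Placebo building: 0.318 + 0.293 × 0.50 = 0.465.

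The bias therefore needs two things: treatment must move the timing, and timing must be associated with the size of the maximum.

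**Equal mean maxima, different timing.** This also satisfies the SAP's null of a zero difference in mean maximum reduction. Across slope SDs of 0.22 to 0.30, the adjusted model estimated +0.08 to +0.24 NPRS and rejected in 6-20% of 44-subject trials, against 5-6% without the covariate.

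**The case against.** The strongest reply concerns size. Without individual slopes the change is at most 15%, and inflation is at most 1%. The large figures appear only after slopes are added, and neither the sample-size assumptions nor the SAP's weekly NPRS code contains a slope term. This stands: the existence of the problem is firm, its size is not. It also follows that the direction for a waning effect depends on the slope variance as well as on the shift in timing. But the documents give no onset profile, and the SAP estimates treatment differences at each of weeks 1 to 4, so it treats onset as open and cannot rely on the harmless case.

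The second reply is limited reach. This is one of 12 secondary endpoints, the unadjusted summaries are kept for both populations, weekly differences are tested elsewhere without the covariate, SAP 8.3 urges caution with secondary tests, and the change is disclosed. All true, and all reasons to rank the point below anything touching the primary analysis. None supplies a valid test of the maximum effect.

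Two technical limits also stand. The simulations used complete data, whereas SAP 10.15.1 sets weeks with fewer than five ratings to missing. Time in days is not exactly 7 × week, because SAP 10.3 gives period 2 a six-day week 2 and ends its week 4 on Day 76. A check with days gave about −21% either way, so this does not matter.

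**Conclusion.** The concern holds. The only inferential analysis of the maximum-effect objective conditions on a variable that treatment can change, so its treatment difference does not in general estimate that objective. It does so when timing is unaffected, for example under a constant effect.

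Otherwise the result can be too small or too large. In the second simulation the error was at most about 0.09 NPRS with common time courses and up to about 0.35 NPRS with individual slopes. These sizes rest on assumed onset profiles and variance splits. Type I error is preserved when there is no effect in any week, but not when only the timing differs.

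The primary week 4 comparison, the week 1-3 comparisons, the sample size and the unadjusted summaries are unaffected. The model should be corrected, as a matter of one secondary endpoint.

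**What to change.** In SAP 11.6.2.3.1, make baseline score the only covariate and change the code to `model <maximum reduction> = <baseline> <study period> <treatment>;`. In Section 12, remove the time term from the bullet that introduces this analysis.

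Keep the random subject term. The subject-by-period term cannot be separated from the residual with one record per subject-period, so retaining or dropping it does not alter the treatment contrast.

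These fixed effects match those the SAP already uses for patient-reported outcomes: "Baseline score within each period by treatment combination will be included as a covariate for all endpoints except PGIC". In the second simulation the model without time recovered the true difference to within about 0.002 NPRS in every scenario.

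Report timing through the summary already planned of the week of maximum reduction by treatment. The cost is one deletion in the text, one in the code and one in Section 12, with no new data or tables.

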11.6.2.4 Patient reported outcomes

Patient Reported outcomes: BPI, SF-MPQ-2, NPSI, BDI-II, PGIC will be considered for secondary efficacy analyses. All analyses will be repeated for Per-protocol and FAS populations.

11.6.2.4.1 *Descriptive Summaries*

Descriptive summaries of patient reported outcomes (BPI, SF-MPQ-2, NPSI, BDI-II) and absolute change from baseline results will be presented by treatment overall and within each study period. Visits to be included in this table are: Baseline, Week 4.

Descriptive summaries as well as number and percentage of subjects reporting each of the categories in PGIC scale (1 - Substantially worse, 2 - Moderately worse, 3 - Slightly worse, 4 - No change, 5 - Slightly improved, 6 - Moderately improved, 7 - Substantially improved) will be summarized by treatment overall and within each study treatment period.

The summaries will be repeated for Per-Protocol and FAS populations.

In DDP: Tables 14.2.5.1, 14.2.5.2, 14.2.6.1, 14.2.6.2, 14.2.7.1, 14.2.7.2, 14.2.8.1, 14.2.8.2, 14.2.9.1, 14.2.9.2

All patient reported outcomes will be listed.

In DDP: Listing 16.2.6.2 to 16.2.6.6

11.6.2.4.2 *Mixed Effects Regression Model*

Mixed effects regression models will be used to compare the absolute change from baseline to week 4 for the patient reported outcomes (BPI, SF-MPQ-2, NPSI, BDI-II, PGIC). The models will have fixed effects for period and treatment. Baseline score within each period by treatment combination will be included as a covariate for all endpoints except PGIC. A random effect for subject will be included to capture the repeated measures nature of the design. Least squares mean changes from baseline and corresponding 95% CI will be presented for LAT8881, Placebo and the difference between LAT8881 vs. placebo overall. The null hypothesis that the difference in least square mean changes from baseline between LAT8881 and placebo across study periods is 0 will be tested. Statistical significance will be declared if the p-value for the difference between treatments < 0.05.

In DDP: Tables 14.2.5.3, 14.2.5.4, 14.2.6.3, 14.2.6.4, 14.2.7.3, 14.2.7.4, 14.2.8.3, 14.2.8.4, 14.2.9.3, 14.2.9.4

```
proc mixed data=;  
  class <subject> <study period> <treatment>; model  
  <change> = <baseline> <study period> <treatment>;  
  random <subject> <subject>*<period>; lsmeans  
  <treatment>/ pdiff;  
run;  
Note that, PGIC will not have <baseline> in the model statement.
```

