All subjects will take their second Day 77 IMP dose in the evening. They will be asked to discontinue their IMP after taking the Day 77 evening dose.

End of Study (Day 91)

At the end of study visit, weight, vital signs, a targeted physical examination, concomitant medications and adverse events will be recorded. Blood and urine samples will be taken for safety analysis.

Early withdrawal

Subjects who withdraw early will be asked to attend an end of study visit. This visit should be scheduled approximately two weeks after the last dose was taken.

Statistical Analysis

With a total sample size of 44 evaluable subjects there is 90% power to demonstrate a statistically significant difference in the mean change from baseline NPRS for the active treatment compared with placebo of at least 1 unit. This assumes that the standard deviation of the change from baseline NPRS is 2, the correlation between active and placebo responses within a subject is 0.5 and there is a 2-sided test at the 5% level of significance. Assuming a 20% dropout rate, it is aimed to enrol at least 55 subjects to obtain 44 evaluable subjects.

The number of subjects within each treatment group is also sufficient to show a statistically significant change from baseline of 2 or more points on the NPRS.

The primary efficacy endpoint is the change from baseline mean NPRS score to the end of treatment mean NPRS score after LAT8881, compared with the change from baseline after placebo treatment. This will be analysed in the per protocol (PP) population, which will be defined in a statistical analysis plan (SAP) before database lock. The PP will be based on the duration of IMP treatment and protocol deviations.

Mixed effects regression models will be used to compare the absolute and percentage changes from baseline to the end of each treatment for the mean NPRS scores. The models will have fixed effects for period and treatment. Baseline mean pain score within each period by treatment combination will be included as a covariate. A random effect for subject will be included to capture the repeated measures nature of the design.

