7.5 Exploratory endpoints

1. *Association between change in mean NPRS from baseline to the end of four weeks treatment and selected subject baseline characteristics, including clinical diagnosis and pre-treatment [REDACTED]*
2. *Change from baseline in [REDACTED] [REDACTED] to the end of 4 weeks treatment, in each treatment period*
3. *Correlation between plasma LAT8881 concentration and the change in mean NPRS from baseline to the end of four weeks treatment in PK subjects*
4. *Change in mean NPRS score from baseline to the last week of each treatment period, after omission of subjects with the 25% most variable first baseline NPRS scores*

8 Statistical Methods

Efficacy endpoints will be summarized in a descriptive manner and analyzed using statistical methods described in section 11.7. The level of significance for statistical tests will be 0.05 and all tests will be two-sided. All p-values will be displayed to four decimal places, with p-values less than 0.0001 presented as '<0.0001' and p-values greater than 0.9999 presented as '>0.9999'. All analyses will be done using SAS [REDACTED]

Safety endpoints will be summarised in a descriptive manner.

Continuous data will be reported using the following descriptive statistics:

1. Number of observations (n)

2. Mean and standard deviation (SD)
3. Minimum (min) and maximum (max)
4. Median

Minimum and maximum values will be reported to the precision of the endpoint reported with maximum of three decimal places; the mean will be presented with one decimal place more and the standard deviation two decimal places more than the precision of the endpoint reported. Categorical data will be presented using frequency (n = number of subjects; m = number of events) and percentage (%).

Listings will be provided for all data recorded in eCRF to study subject profiles. All listings will be sorted by treatment sequence, subject ID, study period and date (if applicable). Unscheduled visit data will only be listed and not included in summaries.

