8.3 Multiplicity Adjustment

Since there is only one primary endpoint defined in the study as per the protocol, multiplicity adjustment is not required. Although, hypothesis tests for secondary and efficacy endpoints will be performed and caution must be taken when interpreting these results. Adjusted p-values using Bonferroni method may be derived for post-hoc analyses if deemed necessary.

9 Analysis Populations

Membership of the analysis populations will be reviewed and finalized during the blind review of the data conducted prior to database lock.

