11.6.1.2 Mixed Effect Regression Model

A mixed effects regression model using a covariance pattern will be fitted to the absolute change from baseline mean NPRS scores at weeks 1, 2, 3 and 4 within each treatment period for the PP population. This analysis will provide the results for the primary efficacy endpoint (change from baseline to week 4) and for the secondary endpoint (change from baseline to weeks 1, 2 and 3).

The model will have fixed effects for period, week, treatment and the interaction between week and treatment. Baseline mean pain score within each period by treatment combination will be included as a covariate. A random effect for subject will be included to capture the repeated measures nature of the design.

Least squares means and corresponding 95% confidence intervals (CI) will be presented for the mean change from baseline for LAT8881, Placebo and difference between LAT8881 vs. placebo at each visit.

P-values for testing the null hypothesis that the difference in least squares means between LAT8881 and placebo at each visit is 0 will be declared statistically significant if the p-value < 0.05.

The covariance pattern will take into account the covariance between observations in different treatment periods and the covariance between observations within the same period (i.e between weeks).

```
proc mixed data=;  
class <subject> <study period> <treatment> <week>; model  
<change> = <baseline> <study period> <week> <treatment>;  
random <subject> <subject>*<period>; lsmeans <treatment>  
<week> / pdiff;  
run;
```

The model will also be fitted to the absolute change from baseline in mean NPRS ratings for the FAS population. Extent of sensitivity analyses of missing data patterns to be undertaken will be decided during the blinded review meeting. In DDP: Tables 14.2.2.1 to 14.2.2.2

11.6.1.2.1 *NPRS at timepoints*

A mixed effects regression model using a covariance pattern will be fitted to the absolute change from pre-dose NPRS scores at timepoints 0.5, 1, 2, 4 and 6 hours post-dose at baseline and week 4 visits within each study period for the per-protocol subjects with NPRS collected at timepoints in baseline and week 4 visits.

The model will have fixed effects for period, week, timepoint and the interaction between week and timepoint. Pre-dose pain score within each week will be included as a covariate. A random effect for subject will be included to capture the repeated measures nature of the design.

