11.6.3 Exploratory Analyses

11.6.3.1

Descriptive summaries of average [REDACTED] will be presented by study period at Baseline and week 4 visits for test and control areas. This summary will be based [REDACTED]

[REDACTED] will be listed by subject.

In DDP: Table 14.2.11.1, Listing 16.2.6.7

11.6.3.1.1 *Mixed Effects Regression Model*

Mixed effects regression models will be used to compare the absolute change from baseline to week

The models will have fixed effects for period and treatment. Baseline score within each period by treatment combination will be included as a covariate. A random effect for subject will be included to capture the repeated measures nature of the design. Least squares mean changes from baseline and corresponding 95% CI will be presented for LAT8881, Placebo and the difference between LAT8881 vs. placebo overall. The null hypothesis that the difference in least square mean changes from baseline between LAT8881 and placebo across study periods is 0 will be tested. Statistical significance will be declared if the p-value for the difference between treatments < 0.05 . See Section 11.6.2.4.2 for SAS program.

In DDP: Table 14.2.11.2

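### Nine secondary LAT8881-placebo contrasts and one exploratory model are to be declared statistically significant at an unadjusted two-sided 0.05, with no order, gate on the primary or nominal label

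*SAP*

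**What the plan says.** There is one primary contrast: absolute change in mean NPRS from baseline to week 4, LAT8881 against placebo, in the per-protocol population (SAP 7.1, 9.2 and 11.6.1.2). The opening of SAP section 8 sets a single level for everything: "The level of significance for statistical tests will be 0.05 and all tests will be two-sided".

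The decision rules that follow are:

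- **SAP 11.6.1.2**, weekly NPRS. The null hypothesis of no LAT8881-placebo difference "at each visit is 0 will be declared statistically significant if the p-value < 0.05". This covers week 4 (the primary) and weeks 1, 2 and 3 (secondary).
- **SAP 11.6.2.3.1**, maximum reduction, and **SAP 11.6.2.4.2**, five patient reported outcomes (BPI, SF-MPQ-2, NPSI, BDI-II, PGIC). In both: "Statistical significance will be declared if the p-value for the difference between treatments < 0.05".
- **SAP 11.6.3.1.1**, the exploratory model. "Statistical significance will be declared if the p-value for the difference between treatments" falls below the same 0.05.
- **Protocol 13.5.1**, NPRS comparisons generally: "Comparisons will be declared statistically significant if p<0.05".
- **SAP 11.6.2.2**, 30% and 50% responders. The p-values are to be reported; no declaration rule is attached.

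SAP 8.3 says no multiplicity adjustment is needed because there is one primary endpoint. It continues: "Although, hypothesis tests for secondary and efficacy endpoints will be performed and caution must be taken when interpreting these results". It ends: "Adjusted p-values using Bonferroni method may be derived for post-hoc analyses if deemed necessary".

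**The concern.** The argument in SAP 8.3 protects the primary test. It does not address what may be said about the other tests, yet section 11.6 gives most of them the same verdict language as the primary. If week 4 NPRS misses, the plan as written still lets the report call an earlier week, the maximum reduction or any of five questionnaires statistically significant.

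That matters here because Protocol 5.2 presents this as the first study of the drug in neuropathic pain, testing whether the concept is sound, with further studies to follow. The same section explains that power was set at 90% to limit false negatives. The plan has no matching limit on false positive secondary claims, which could be read as evidence of efficacy after a negative primary.

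**Working it through.** **1. The plan's own figure, to confirm the level of the primary test.** The protocol synopsis states: "With a total sample size of 44 evaluable subjects there is 90% power to demonstrate a statistically significant difference". Inputs from the synopsis and Protocol 13.2: difference 1, SD of change 2, active-placebo correlation 0.5, two-sided 5%.

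- SD of the within-subject difference = √(2 × 2² × (1 − 0.5)) = 2.
- Normal approximation: n = (2 × (1.960 + 1.282) / 1)² = 42.03, so 43.
- Paired t with the noncentral t distribution: power at n = 44 is 90.0%.
- Dropout: 44 / 0.80 = 55.

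The stated 44 and 55 reproduce. The primary is one test at two-sided 5%, and nothing below changes that.

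**2. Count of secondary contrasts.** Explicit declaration rule in the SAP: 3 (weeks 1-3) + 1 (maximum reduction) + 5 (patient reported outcomes) = 9. The two responder endpoints, tested at the general 0.05 level but only reported, bring the total to 11.

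Not counted:

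- the percentage-change models in SAP 11.6.2.1, which refit the same diary data;
- the repeats in the FAS;
- the timepoint model in SAP 11.6.1.2.1, which has no treatment term.

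The weekly contrasts follow the text of SAP 11.6.1.2. The sample code printed there omits the week-by-treatment term needed to produce them.

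**3. Chance of at least one p < 0.05 when the drug has no effect on any endpoint.** The documents give no correlation between endpoints, so it is an assumption and is varied. The protocol's 0.5 is the correlation between a subject's active and placebo responses, a different quantity.

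- Independent tests: 1 − 0.95^k in either direction, and 1 − 0.975^k in favour of LAT8881.
- Equal correlation ρ between normal test statistics, with U standard normal: 1 − E[{Φ((1.96 − √ρ U)/√(1 − ρ)) − Φ((−1.96 − √ρ U)/√(1 − ρ))}^k]. For the drug's favour only, drop the second Φ term.

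| Assumed ρ | 9 tests, either direction | 9 tests, favouring LAT8881 | 11 tests, either direction | 11 tests, favouring LAT8881 |
|---|---|---|---|---|
| 0 | 37.0% | 20.4% | 43.1% | 24.3% |
| 0.3 | 32.6% | 16.5% | 37.5% | 19.1% |
| 0.5 | 26.9% | 13.5% | 30.4% | 15.2% |
| 0.7 | 20.2% | 10.1% | 22.3% | 11.1% |
| 0.9 | 12.4% | 6.2% | 13.1% | 6.6% |

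**4. A less uniform correlation pattern.** This simulation used 400,000 draws and 11 secondary tests plus the primary. Assumed correlations were 0.7-0.8 among the NPRS-derived tests, 0.4-0.6 among the patient reported outcomes and 0.3-0.5 between the two groups. At least one secondary p < 0.05 occurred in 25% to 32% of draws. In 21% to 28% it occurred with a non-significant primary, which is the case of concern. In favour of LAT8881 only, regardless of the primary, it was 13% to 16%.

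**5. What control would do.** Testing secondaries only after a significant primary holds the chance of any declaration under the global null to at most 5%. So does Bonferroni, at 0.05/9 = 0.0056 for nine tests or 0.05/11 = 0.0045 for eleven. A nominal label leaves the probabilities in the table unchanged and alters only what may be claimed.

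**The case against.** The strongest case for the plan is this. It names one primary endpoint, says openly that secondary tests are unadjusted and tells the reader to be cautious. The 5% in SAP section 8 is a per-test level, and no family-wise rate is promised for secondary endpoints, so no promise is broken. In a phase IIa study, formal control over secondary endpoints is a choice, and many sponsors would not make it.

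Much of that stands. Formal adjustment is not required here, and declaring p < 0.05 while interpreting it cautiously is a tension, not a flat contradiction. But caution sets no rule. An analyst following section 11.6 would have to write that a questionnaire difference is statistically significant, and section 8.3 would give no ground for writing anything else. The Bonferroni sentence does not help, because it is optional and limited to post-hoc analyses.

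A reader might infer three stronger things that the documents do not support:

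- *That the trial's 5% error rate is compromised.* It is not, because the primary contrast is single and prespecified.
- *That at least eleven comparisons are each declared significant.* The SAP's declaration rule reaches nine. SAP 11.6.2.2 only reports the responder p-values. Protocol 13.5.1 states its rule in general terms, but the SAP does not carry it into the responder section.
- *That an ineffective drug has a 30% chance of a declared secondary benefit.* That figure needs eleven tests and an assumed correlation of 0.5, and half of it is in placebo's favour.

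**Conclusion.** The concern holds for secondary and exploratory claims only. Nine secondary LAT8881-placebo contrasts, and one exploratory model, carry an unadjusted rule to declare significance, with no order, gate or nominal label, and SAP 8.3 does not settle how those declarations are to be read.

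Under no effect on any endpoint, the chance of at least one declared difference among the nine is about 27% at an assumed equal correlation of 0.5, ranging from 12% (correlation 0.9) to 37% (independence). In favour of LAT8881 it is about half that: 13.5%, range 6% to 20%. Adding the two responder endpoints gives 30% (13% to 43%). These figures rest on approximately normal test statistics and on correlations that the documents do not supply, so the range should be quoted with the central value. Even the lowest two-sided figure, 12.4%, is more than twice the 5% of a single test. The point is worth correcting, but it does not threaten the primary conclusion.

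**What to change.** Before database lock:

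- **SAP 8.3:** state that *statistically significant* is reserved for the week 4 absolute NPRS change contrast in the per-protocol population at two-sided 0.05. State that all secondary, exploratory and FAS p-values are nominal and are reported with estimates and 95% confidence intervals.
- **SAP 11.6.1.2 (weeks 1-3 only), 11.6.2.3.1, 11.6.2.4.2 and 11.6.3.1.1:** replace the declaration sentences to match. Keep the rule for week 4 in the per-protocol population.
- **Protocol 13.5.1:** leave its rule in force, because it also governs the primary contrast. Record in SAP section 12 that it is restricted to that contrast.
- **Optional:** if the sponsor wants a formal secondary claim, prespecify a short sequence tested only after a significant primary, with everything outside it nominal.

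SAP 11.6.2.1 and 11.6.2.2 contain no declaration sentence, so the statement in 8.3 covers them. The Bonferroni sentence concerns post-hoc analyses and can stay.

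The cost is SAP wording. No new data, analyses or subjects are needed. The downside is that an isolated secondary p-value below 0.05 can no longer be called significant.
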